8.2 Hypotheses and Statistical Analyses

The Figure shows graphically how our hypotheses relate to one another. Hypothesis 1 tests the combined effects of paths A, B, C, D & E i.e., the total effect of BP on mobility. Hypothesis 2 tests path A, Hypothesis 3 tests path D, Hypothesis 4 tests path B+E; together Hypotheses 2, 3 and 4 together test the effect of BP on mobility mediated through BP's effects on WMH and WM microstructure. Hypothesis 5 tests the relative importance of paths A and B to that of path C, i.e., the degree to which the effect of BP on mobility is explained by WMH. Hypothesis 6 tests the relative importance of paths D and E to that of path C, i.e., the degree to which the effect of BP on mobility is explained by changes in WM microstructure.

Hypothesis path diagram

Hypothesis 1: Intensively treating 24-h systolic BP to a goal of <130 mmHg versus standard BP control of <145 mmHg will lead to faster walking speeds at T₃₆. (Paths A&B+C+D&E)

Hypothesis 2: Intensively treating 24-h systolic BP to a goal of <130 mmHg versus standard BP

control <145 mmHg will lead to smaller total WMH volume. (Path A)

Hypothesis 3: Intensively treating 24-h systolic BP to a goal of <130 mmHg versus standard BP

control <145 mmHg will stabilize brain WM microstructural integrity (FA and MD) at T₃₆. (Path

D) We will perform 3 sets of analyses for hypotheses 1, 2 & 3:

- a. Multiple linear regression will be performed with treatment group (intensive vs. standard) as the predictor of interest. Gait velocity at T₃₆ is the primary outcome for hypothesis 1, WMH at T₃₆ is the primary outcome for hypothesis 2, and DTI indices (FA and MD) are the primary outcomes for hypothesis 3. The analysis will be intention-to-treat. Age, sex, and 24 hour SBP at T₀ (baseline) will be included as covariates, along with other demographic factors for which the treatment groups are not comparable. **The analysis for hypothesis 1 is the proposal's primary efficacy analysis and thus the proposal is powered to address this analysis (see Sample size estimation).**

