Other mobility measures will also be examined as secondary outcomes in models otherwise identical to those in a, b, and c. The analyses will be repeated for cognition, with the speed obtained on Trailmaking B at T_{36} as the primary outcome and other cognitive measures as secondary outcomes. Additional secondary analyses will use logistic and ordinal models with the same predictors and incontinence presence and severity, respectively as outcomes; the progression model (c) will be fit as binary or ordinal generalized linear mixed models.

Hypothesis 4: Reduced total WMH and decreased markers of tissue damage on DTI at T_0 and at T_{36} are linked to better mobility at T_{36} . (Paths B+E)

The same outcomes will be used for this hypothesis as in hypothesis 1, with identical analyses except that WMH, and DTI indices (FA and MD) as continuous variables will be the primary predictor of interest. The power for this hypothesis as expressed as increased in explained variability (R^2) will be the same as for hypothesis 1: 85% power to achieve an increase in R^2 of 0.0533; we actually observed an increase in R^2 of 0.1658, to 0.2925, as the effect of tWMH, corresponding to a reduction in gait

velocity of 0.0063 m./sec. for each 0.1% increase in tWMH. The analyses will be repeated for gait velocity at T₁₈ with a model corresponding to analysis b, and for the following progression model replacing the model for analysis c:

$$Y_{i0} = b_{i0} + \beta_C (X_{i0}) + \text{cross sectional covariates} + \text{residual error}$$

$$Y_{i18} = b_{i0} + \beta_C (X_{i0}) + \beta_L (X_{i18} - X_{i0}) + \text{cross sectional covariates} + \text{longitudinal covariates} + \text{residual error}$$

$$Y_{i36} = b_{i0} + \beta_C (X_{i0}) + \beta_L (X_{i36} - X_{i0}) + \text{cross sectional covariates} + \text{longitudinal covariates} + \text{residual error}$$

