Product of coefficients methods^{35,36} will be used for formal statistical inference regarding the mediation. Specifically, we will estimate the product of the effect estimated for hypothesis 2 corresponding to Path A (the effect of intervention group on total WMH at T₃₆), and the effect estimated for hypothesis 3 corresponding to Path B (the effect of WMH at T₃₆ on gait velocity at T₃₆). The magnitude of this product turns out to be proportional to the change in the effect of intervention group on gait velocity at T₃₆ when WMH at T₃₆ is added to a regression model of gait velocity at T₃₆ as a function of intervention group. Similar models will be used to assess outcomes at T₁₈, and the cognitive outcomes. As formal tests for mediation using the product of coefficients method require larger sample sizes than available in this study, we will treat results from analyses in Hypothesis 5 as preliminary, to be potentially verified by a larger study should the main effects in Hypotheses 1-3 be confirmed.

Hypothesis 6: Diffusion tensor imaging (DTI) indices (FA, MD) at T₀ and at T₃₆ mediate the effect of treatment group, showing that the mechanism by which reduced ABP is linked to better mobility occurs by preserving brain WM microstructural integrity (FA, MD).

(Paths C – D&E) The same analysis as used for hypothesis 5, except that the mediating effect of the DTI indices will be assessed.

Missing Data.

Death and study attrition are associated with age-related diseases. Failure to account for this informative censoring may result in biased estimates of dementia risk and cognitive decline.³⁷ Hence, we will collect data by telephone to assess the degree to which living participants who fail to appear for their final assessment differ from participants who complete the study. As mentioned above, we will use telephone administration of a validated mobility assessment³⁹ and the method developed by [name] and colleague³⁰ to estimate mobility outcomes through multiple imputation or joint modeling that would have been

observed had the participants appeared for their clinical assessment. While our primary efficacy outcome analysis will be limited to participants who complete the study, this will be the first trial in aging with the potential to assess the impact of informative dropout beyond usual sensitivity analyses.

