Here, x_i is the treatment group indicator for participant i (one for intervention, zero for comparison); Y_{i1} is the SF-36 score for participant i at time 1 (baseline); Y_{i2} is the SF-36 score for participant i at time 2 (36 month follow-up); β_0 is interpreted as the average SF-36 score at baseline in the reference group; β_C is interpreted as the difference in the average SF-36 score at baseline between the intervention group and the reference group and will be zero if the two groups are exactly comparable in their baseline values; β_L is interpreted as the average change in SF-36 between 36 month follow up and baseline in the reference group; β_T is interpreted as the difference average change in SF-36 between 36 month follow up and baseline between the intervention group and the reference group and thus the parameter of primary interest; γ_i is a random intercept for participant i that addresses the correlation in SF-36 across the two time points; and ε_{i1} and ε_{i2} are the residual error terms at baseline and follow-up, respectively. Above analysis will be repeated for Sleep Scales (Pittsburgh Sleep Quality Index, and Epworth Sleep scale), and then as stratified analyses (b - e below) for both Sleep and SF-36 scales.

- b. Stratified according to < or > median age
- c. Stratified according to gender
- d. Stratified according to years of education
- e. Stratified according to a clinical diagnosis of minor or major depression
- f. Change from baseline in cognitive variables
- g. Changes from baseline in mobility parameters
- h. Changes from baseline in urinary function
- i. Change from baseline in WMH (%)

6. Regression of changes from baseline in WMH as a mediator of changes from baseline in mobility, cognition, urinary function and depressive symptoms. These analyses will be based on the analyses in (2) and (3), but with the addition of mediation by and interaction with WMH using the methods of Vanderweele (REF below).

$$Y_{i1} = \beta_0 + \beta_C x_i + \gamma_i + \varepsilon_{i1}$$

$$Y_{i2} = \beta_0 + \beta_C x_i + \beta_L + \beta_T x_i + \gamma_i + \theta_M (m_{i2} - m_{i1}) + \theta_{INT} x_i (m_{i2} - m_{i1}) + \varepsilon_{i2}$$

$$m_{i2} - m_{i1} = \alpha_0 + \alpha_1 x_i + \delta_i$$

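### The protocol's product-of-coefficients rule points to the wrong hypothesis for its mediator slope, and the only slope it defines omits treatment arm; the SAP corrects this for WMH at 36 months but not for DTI or month 18

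*Protocol*

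**What the plan says.** In Protocol Section 8.2 (Hypotheses and Statistical Analyses), the product for hypothesis 5 has two factors. The first is "the effect estimated for hypothesis 2 corresponding to Path A", the arm effect on total WMH at T36. The second is "the effect estimated for hypothesis 3 corresponding to Path B", described there as the effect of WMH on gait velocity at T36. The opening of the same section assigns the paths differently: "Hypothesis 3 tests path D, Hypothesis 4 tests path B+E".

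Hypothesis 4 uses the hypothesis 1 outcomes "with identical analyses except that WMH, and DTI indices (FA and MD) as continuous variables will be the primary predictor of interest". For hypotheses 1 to 3, age, sex and baseline 24-hour systolic BP "will be included as covariates, along with other demographic factors for which the treatment groups are not comparable". Arm is the predictor of interest there, not a covariate. Under hypothesis 4 it returns only in secondary interaction analyses.

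The protocol adds that the product is proportional to the change in the arm effect on gait when WMH enters a model with arm. It plans similar models at T18 and for cognition. Hypothesis 6 (FA and MD) is "The same analysis as used for hypothesis 5, except that the mediating effect of the DTI indices will be assessed".

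SAP item 6, dated before the planned database lock, covers "Regression of changes from baseline in WMH as a mediator of changes from baseline in mobility" and other functions. Its outcome equation holds arm, WMH change and their interaction together, using baseline and 36 months, with bootstrap inference. The SAP has no mediation model for DTI. Item 4 f–h relates DTI change to function but does not split the arm effect into direct and indirect parts.

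**The concern.** The rule cannot be run as written, because hypothesis 3 supplies no WMH slope. An analyst would go to hypothesis 4, the only place where a Path B or Path E slope is defined, and take a slope from a model without arm. If arm affects gait by any route other than the mediator, part of that direct effect is absorbed into the slope. The product then no longer matches the change in the arm effect that the protocol says it tracks.

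At stake is the mechanistic claim. When direct and indirect effects point the same way, the error favours the conclusion that white-matter change explains the functional benefit.

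**Working it through.** **Inputs** (Protocol 8.2 and 8.3, prior observational study unless noted)
- Gait R²: 0.1267 with covariates only; arm adds 0.1082 (to 0.2349); WMH adds 0.1658 (to 0.2925).
- WMH R²: 0.1162 with covariates only; arm adds 0.0861 (to 0.2023).
- Arm effect on gait: 0.15 m/s, falling to 0.10 m/s once WMH is added. Arm effect on WMH: 0.93%.
- Gait slope on WMH: 0.0063 m/s per 0.1%, that is 0.063 m/s per 1%.
- Design increments: 0.0533 (gait) and 0.0540 (WMH), with 140 completers and 85% power.

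**1. The plan's power figure.** f² = 0.0533/(1 − 0.1800) = 0.065 and λ = 140 × 0.065 = 9.1. With 1 and 135 degrees of freedom and alpha 0.05 (assumed; not stated), power is 84.97%. For WMH it is 85.01%. Both reproduce the stated 85%.

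**2. Was arm in the prior-study WMH slope model?** 0.2925 − 0.1658 = 0.1267, the covariates-only base. With arm in the model, the base would have been 0.2349.

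**3. Identity.** Let a be the arm effect on the mediator and c′ the direct arm effect. Let b be the mediator slope with arm in the model and b₀ the slope without it. In linear regression, given the covariates,

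a·b₀ = a·b + c′ × (partial R² of arm with mediator).

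Only a·b equals the change in the arm effect.

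**4. Numbers in.**
- Partial R² = 0.0861/(1 − 0.1162) = 0.097.
- Product without arm: 0.93 × 0.063 = 0.0586 m/s; 0.0586/0.15 = 39%.
- Gap: 0.10 × 0.097 = 0.0097 m/s.
- Product with arm: 0.0586 − 0.0097 = 0.049 m/s; 0.049/0.15 = 33%.
- Stated change: 0.15 − 0.10 = 0.050 m/s; 0.050/0.15 = 33%.
- Check from the R² increments alone: c′ = 0.102 m/s, product 0.048 m/s with arm and 0.0580 m/s without.

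The overstatement is 17% (0.0586/0.050) to 21% (0.0580/0.048).

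**5. No mediator effect (b = 0).** The whole arm effect is then direct, so the expected product is the arm effect times the partial R².
- Observed effects: 0.15 × 0.097 = 0.0146 m/s, 9.7% of the arm effect.
- Design effects: the arm effect scales to 0.15 × √(0.0533/0.1082) = 0.105 m/s; partial R² = 0.0540/0.8838 = 0.061; product 0.0064 m/s, 6.1%.

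**6. False positives with b = 0** (simulation, N = 140, 20,000 runs, alpha 0.05 assumed)

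| Setting | Joint test, arm omitted | Joint test, arm included | Sobel, arm omitted | Sobel, arm included |
|---|---|---|---|---|
| Observed effects | 24% | 4.8% | 16% | 2.3% |
| Design effects | 10% | 4.1% | 4.5% | 1.2% |
| No direct arm effect | 4.9% | 4.9% | 2.1% | 2.3% |

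**The case against.** The wrong hypothesis number may be a numbering slip. The protocol describes mediation as adding a mediator to a model that already contains the predictor, and says the product tracks the change in the arm effect. Both fit an arm-adjusted slope. This stands as a plausible reading of intent, but no arm-adjusted Path B or Path E slope is defined anywhere in the protocol.

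The R² step describes the earlier cohort with simulated arms. It shows what that regression contained and supports the reading of hypothesis 4, but it does not prove how the trial model will be fitted.

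A reader might infer that the trial's WMH mediation result at 36 months will be biased. The documents do not support that: SAP item 6 puts arm in the outcome equation. However, the SAP presents its items as added secondary analyses and does not withdraw the protocol rule. Two WMH rules therefore coexist, one on T36 levels and one on change from baseline.

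A reader might also infer that the rule reports mediation whenever there is none. It does not. The error is zero if arm has no direct effect or does not move the mediator. It takes the sign of the direct effect, so it understates mediation when direct and indirect effects oppose.

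Finally, the protocol calls the hypothesis 5 results preliminary, and the secondary objectives name mediation by WMH only. This limits the consequence. But the reason given for that label is sample size, and a larger study using the same slope would repeat the bias.

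**Conclusion.** The point holds in limited form. The hypothesis label is wrong, and the only mediator slope the protocol defines does not give the quantity it claims. On the prior-study WMH figures the product is about one fifth too large (0.059 against 0.049–0.050 m/s). With no mediator effect, its expected value is about 6% to 10% of the arm effect.

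The defect remains in three places: DTI mediation (hypothesis 6), the T18 mediation models, and the unreconciled difference between protocol and SAP for WMH. The WMH figures only illustrate its size. The documents give no DTI effect sizes, so none can be stated for FA or MD.

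The figures assume linear models, prior-study R² values carried over to the trial, and rounded inputs; the power and false-positive figures also assume alpha 0.05. The primary efficacy analysis (hypothesis 1) and the comparison of arm effects with and without WMH are unaffected. The change should be made, but the trial's main conclusion does not depend on it.

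**What to change.** - In Protocol 8.2, under hypothesis 5, change the source of Path B from hypothesis 3 to hypothesis 4.
- Require the Path B and Path E slopes to come from a gait model containing arm, the mediator and the listed covariates, at T36 and, if those analyses are kept, at T18.
- State that SAP item 6 governs WMH mediation.
- Add FA and MD versions of the item 6 outcome and mediator equations, with bootstrap intervals, for hypothesis 6.
- In those versions, compute the mediated share from INT_MED + PIE only. The SAP's numerator for the proportion mediated also includes INT_REF = θ_INT × α₀. That term does not involve α₁, the arm effect on the mediator, so the share can be non-zero when arm leaves the mediator unchanged.

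The cost is wording, one more covariate and a few more bootstrap runs. If direct and indirect effects point the same way, the reported mediated share becomes somewhat smaller.

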Here, Y_{i0} , Y_{i18} , and Y_{i36} are the outcomes (mobility or imaging) at T₀, T₁₈ and T₃₆ for study participant i , X_{i0} , X_{i18} , and X_{i36} the tWMH at T₀, T₁₈ and T₃₆ for study participant i , and b_{i0} is a random intercept that is used to take into account the fact that repeated measurements on individuals are not independent. The model will be fit as a linear mixed model³⁷. Again the other β_j 's are fixed effects although we will consider the possibility that treating them as random effects will add to the model fit. The parameters of interest are β_C and β_L , the cross-sectional and longitudinal effects of the imaging measures on mobility over the 36-month follow-up. As secondary analyses we will consider interactions with treatment group and nonlinear effects in time. Analyses will be repeated for the other mobility and cognitive measures, also as linear mixed models, and urinary incontinence presence/severity as binary and ordinal generalized linear mixed models.

Hypothesis 5: Total WMH at T₀ and at T₃₆ mediate the effect of treatment group, showing that

the mechanism by which reduced ABP is linked to better mobility occurs by reducing total WMH.(Paths C - A&B) Mediation models allow the evaluation of hypotheses using biological mechanisms. In this case, we believe that much of the salutary effect of reduced ABP results from reduced WMH. Assessing mediation involves estimating direct effects (Path C, above) and indirect effects (Paths A and B, above) in multistage predictor models by adding potential mediators to models describing the effect of a predictor on the outcome. To the extent by which WMH mediates the effect of BP, the effect of BP will be reduced in the model that includes WMH compared to the model not including WMH. We saw this in our observational study, as the adjusted effect of SBP in the pseudo-treatment group was reduced

from a .15 m/sec. to a .1 m/sec. difference in gait velocity when WMH was added as a model predictor.

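### Hypotheses 5 and 6 are each defined against direct path C, but each adds only one imaging mediator, so the treatment effect left over is not C

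*Protocol*

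**What the plan says.** Protocol section 8.2 (Hypotheses and Statistical Analyses) describes a path diagram. The diagram is not shown in the copy reviewed, but the text names its paths: A and B through WMH, D and E through white-matter microstructure (the DTI indices FA and MD), and a direct path C. It names no path between the two markers.

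- Total effect: "Hypothesis 1 tests the combined effects of paths A, B, C, D & E i.e., the total effect of BP on mobility".
- Hypothesis 5: "Hypothesis 5 tests the relative importance of paths A and B to that of path C".
- Hypothesis 6: "Hypothesis 6 tests the relative importance of paths D and E to that of path C".

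The text under hypothesis 5 identifies the direct effect with path C: "Assessing mediation involves estimating direct effects (Path C, above) and indirect effects (Paths A and B, above) in multistage predictor models by adding potential mediators". The operation it then specifies has one mediator: "the effect of BP will be reduced in the model that includes WMH compared to the model not including WMH". Formal inference uses the product of paths A and B, which is tied to the change in the arm effect when T36 WMH "is added to a regression model of gait velocity at" T36. Hypothesis 6 is "The same analysis as used for hypothesis 5, except that the mediating effect of the DTI indices will be assessed".

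Hypothesis 4 (paths B and E) uses WMH and the DTI indices as predictors of mobility, but they replace treatment group as the predictor of interest. SAP item 6 has WMH change as its only imaging mediator, and defines its controlled direct effect with respect to WMH alone. The other candidates there (age, sex, 36-month ambulatory systolic BP) replace WMH one at a time. The SAP has no DTI mediation model.

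**The concern.** Two hypotheses share one reference quantity, path C, and neither analysis estimates it. When WMH alone is added to the treatment model, any benefit that reaches gait through microstructure and is not captured by WMH stays in the arm coefficient. When DTI alone is added, the same happens with the WMH route.

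If WMH and the DTI indices are correlated within arm, each single-mediator slope also picks up part of the other marker's effect, so that part is counted in both mediated effects. A correlation is plausible. Protocol section 5.6 measures FA and MD inside WMH areas as well as in normal-appearing white matter, and plans to characterise their association with WMH.

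At stake is the mechanistic reading of the trial: how much of any gait benefit runs through the measured imaging routes, and how much does not.

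**Working it through.** **The plan's own figures.** The prior cohort's arm-type difference went "from a .15 m/sec. to a .1 m/sec. difference in gait velocity when WMH was added as a model predictor". That is (0.15 − 0.10)/0.15 = 33% attenuation in a WMH-only model. The power statement for hypothesis 1 also reproduces: f² = 0.0533/(1 − 0.1800) = 0.065, noncentrality 140 × 0.065 = 9.1, 1 and 135 degrees of freedom, two-sided alpha 0.05 (assumed; none is stated), power 84.97% against the stated 85%.

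**Algebra.** Assume linear models without arm-by-mediator interaction, mediators standardised within arm, DTI scored in the same direction as WMH (higher is worse), and within-arm correlation r. Write the path coefficients as A, B, C, D, E.

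- Gait = C·arm + B·WMH + E·DTI, so Total = AB + C + DE.
- Given arm and WMH, the expected DTI is (D − rA)·arm + r·WMH.
- WMH-only model: indirect effect A(B + rE), remaining arm effect C + DE − rAE.
- DTI-only model: indirect effect D(E + rB), remaining arm effect C + AB − rDB.

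The WMH-only remainder equals C only if E = 0 or D = rA; the mirror condition holds for DTI. The amount r(AE + DB) is the excess of the two separate indirect effects, added, over the joint indirect effect AB + DE.

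**Illustration 1: equal parallel mediators, AB = DE = C = one third of the total.** Single-mediator share = (1 + r)/3; apparent C share = 1 − (1 + r)/3.

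| r | Share per marker | Sum of the two | Apparent C share | True C share |
|---|---|---|---|---|
| 0 | 33% | 67% | 67% | 33% |
| 0.3 | 43% | 87% | 57% | 33% |
| 0.5 | 50% | 100% | 50% | 33% |
| 0.7 | 57% | 113% | 43% | 33% |

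**Illustration 2: calibrated to the cohort's 0.15 and 0.10 m/s, mediators again equal.** Each single-mediator model then reports an indirect effect of 0.05 and a remainder of 0.10 m/s at every r. Since A(B + rE) = AB(1 + r) = 0.05, AB = 0.05/(1 + r) and C = 0.15 − 0.10/(1 + r).

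| r | True C (m/s) | Reported remainder (m/s) | Joint indirect (m/s) | Sum of separate indirects (m/s) |
|---|---|---|---|---|
| 0 | 0.050 | 0.100 | 0.100 | 0.100 |
| 0.3 | 0.073 | 0.100 | 0.077 | 0.100 |
| 0.5 | 0.083 | 0.100 | 0.067 | 0.100 |
| 0.8 | 0.094 | 0.100 | 0.056 | 0.100 |

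A simulation with 2,000,000 subjects per row agrees. At r = 0.5 both single-mediator remainders are 0.0999, and the joint model returns 0.0833 against a true 0.0833.

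**Illustration 3: DTI has no effect of its own (E = 0), A = D, AB = 0.05 and C = 0.10 m/s.** The DTI-only model still credits DTI with 0.05r: 0.015, 0.025 and 0.040 m/s at r = 0.3, 0.5 and 0.8, which is 10%, 17% and 27% of 0.15 m/s. Its remainder is 0.135, 0.125 and 0.110 m/s against a C of 0.10.

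The two faults pull in opposite directions in Illustration 2. At r = 0 nothing is counted twice, but the remainder is furthest from C. As r rises, the remainder approaches C and the double counting grows.

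**The case against.** The best defence is that section 8.2 also explains hypotheses 5 and 6 as asking how far the BP effect is explained by the one marker named. A single-mediator attenuation does answer that, so on this view only a label is wrong. This stands for the per-marker question. It does not rescue the comparison with path C, which the same sentences state and which the hypothesis 5 text repeats.

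Three stronger readings are tempting, and the documents do not support them.

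- A reader might infer that the reported shares will exceed 100%. That needs someone to add them, and nothing in the plan says they will be added or ranked. In Illustration 1 it also needs r above 0.5; in Illustration 2 the sum stays at 0.100/0.15 = 67%.
- A reader might infer that both markers will look like strong mediators when only one is. In Illustration 3 the inert marker gets 10% to 27% against 33% for WMH, and only if treatment moves DTI as much as WMH.
- A reader might infer that the trial's main conclusion is exposed. Hypothesis 1 uses no mediator.

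Two further points have force. The protocol already calls hypothesis 5 results preliminary, but the reason given is sample size. A larger study with the same models would have the same bias, and the caveat does not name hypothesis 6. Also, a joint model does not by itself separate the markers: section 5.6 will examine FA and MD as early indicators of WMH accrual, so DTI damage may precede WMH. Marker-specific parts then depend on an assumed ordering. The joint mediated effect and C do not.

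The protocol also says that hypotheses 2, 3 and 4 together test the combined mediated route. That is a set of separate tests, not an estimate of the joint effect or of C.

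**Conclusion.** The concern holds in a limited form. As specified, neither hypothesis 5 nor hypothesis 6 estimates the path C it is defined against, except in special cases such as an omitted marker with no effect of its own. If the markers are correlated within arm, their separate mediated effects overlap and should not be added or compared.

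The size is unknown, because the documents give neither a WMH-DTI correlation nor a DTI effect on gait. The illustrations assume equal parallel mediators (or, in the third, an inert DTI marker) and linear models. Under them the leftover effect overstates C by between 0.006 m/s (r = 0.8) and 0.050 m/s (r = 0) on the cohort's 0.15 m/s scale. The SAP does not close the gap: its direct effect contains any DTI route not captured by WMH. The fault is confined to secondary mechanism analyses, but it is bias, and it can be removed with data the trial already collects.

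**What to change.** Add one outcome model of T36 gait on arm, WMH and DTI together (FA and MD, or one summary named in advance), with an arm model for each mediator. Report first the joint mediated effect and path C, with patient-level bootstrap intervals. Carry the same model into SAP item 6 by adding DTI change beside WMH change; if the arm-by-WMH interaction is kept there, state whether an arm-by-DTI interaction is included.

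Report WMH-specific and DTI-specific parts only under a stated WMH-DTI ordering. If single-mediator results are kept, label each remainder *not through this marker*, and say that the two shares are not to be added or compared.

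The cost is wording and analysis code, with no new data. The downside is wider intervals when the markers are highly correlated, with about 140 completers expected. The joint model still assumes no unmeasured common causes of the mediators and gait, as the single-mediator models do, and the SAP should say so.
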